The therapy pod is powered by a Lithium-Ion battery that provides 30-40 hours of therapy (4-7 days of typical use) if fully charged. The battery can be recharged in 2-3 hours by plugging the device into an AC adapter.

3. Study Design

The study is a single site, double blinded, placebo controlled randomized clinical trial. 40 subjects will be selected based on the inclusion criteria stated below and then randomized to either the intervention group or the placebo control group. Prior to the start of this study, a Controlled Substance Utilization Review and Evaluation (CURES) reports will be acquired to establish baseline number of opioid prescriptions for each subject. Subjects will track how consistently they are using pain medications, both opioids and non-opioids, during the two weeks prior to the start of the study. They will also provide twice daily recordings of their pain intensity via a mobile application. At the end of this two-week period, each subject will be fitted with a Quell or a sham device, including initial calibration to the subject's comfort level as described in the background section.

The sham device is identical to Quell in all aspects with one exception. While Quell delivers 1 hour of continuous stimulation during a therapy session, the sham device delivers three 2-minute periods of stimulation at 0, 28 and 58 minutes within the therapeutic session. This limited stimulation should have little to no analgesic effect but should suggest to the subject that they are receiving therapy.

Neither the principal investigator, nor the co-investigator or the subject will know if they are given a sham device or the actual Quell device. The study coordinators will be the only ones who will be aware of which intervention subjects receive. At the end of the study, subjects will be asked if they thought they had the sham or actual device. Both the principal and the co-investigator will be asked to identify which subjects they thought had Quell vs the sham device, prior to analysis of the data.

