40 Subjects with a diagnosis of metastatic cancer of any type, with cancer related pain on active chemotherapy treatment, who meet the inclusion and exclusion criteria will be selected for participation in this study

General Inclusion Criteria:

- 1. Male or Female greater than or equal to 18 year of age at visit one.
- 2. Documented diagnosis of metastatic cancer, who has cancer/chemotherapy related pain, with a prognosis of 6 month or greater as determined by the primary oncologist.

- 3. Visual evidence that subject owns a smart phone and is able to use basic mobile applications such as downloading an app, opening the app, and performing one simple task within the app.
- 4. Subject speaks and reads English fluently.
- 5. Subject able to understand and grant informed consent.
- 6. Live in an area with cellular data connectivity available as provided by the subject.
- 7. Documented adherence with clinic follow up visits per medical records.
- 8. Subject using at least one opioid medication on a daily basis.

Exclusion Criteria:

- 1. Subject has a cardiac pacemaker, implanted defibrillator or other implanted electronic device.
- 2. Inability to complete subjective data as required; e.g. on mobile application and questionnaires.
- 3. Does not live in an area with suitable cellular data connectivity.
- 4. Has infrequent scheduled clinic visits.

Subject Recruitment

Subjects will be recruited from the Scripps Mercy Oncology Clinic, San Diego California.

6. Concurrent Medications

All subjects should be maintained on their same oncology treatment protocol as directed by the primary oncologists during the study as they were prior to the onset of the study. Any changes in medication type, doses and frequency should be discussed with the treating physician and documented.

7. Study Procedures

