7.1 Enrollment

Subjects meeting eligibility criteria will be screened by the primary investigator and treating oncologist. Subjects will be introduced to the study during their scheduled oncology and or palliative care visit. Study information will be made available to the subjects. Those interested in the study will be provided with the informed consent, enrolled in the study and provided with the materials necessary for participation in the study.

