7.3.1 Concomitant Medications

All concomitant medications and concurrent therapies will be documented at screening and each scheduled clinic visit. A CURES report will be retrospectively generated for one month at time of enrollment, then every four weeks for the duration of the study.

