8.2 Visit 2 (Week 2)

- 1. Record any Adverse Experiences as needed.
- 2. Review Mobile Application Pain assessment.
- 3. Review documentation of analgesic use.
- 4. Perform and record vital signs.
- 5. Give subject Quell/Sham device, make sure subject properly calibrates.
- 6. Educate subject on how to use the device and to adjust intensity if needed and communicate that stimulation should feel "strong but comfortable".
- 7. Schedule follow up phone calls for subject to help trouble shoot and field questions on the device.
- 8. Perform and record the SF-MPQ-2.
- 9. Perform and record the results of the MOS Sleep Scale.
- 10. Schedule follow up visit for 2 weeks.

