11.3 Protocol Violations

A protocol violation occurs when the subject, investigator, or Sponsor fails to adhere to significant protocol requirements affecting the inclusion, exclusion, subject safety and primary endpoint criteria. Protocol violations for this study include, but are not limited to, the following:

- Failure to meet inclusion/exclusion criteria
- Use of a prohibited concomitant medication

• Include other specific examples as appropriate for the study (non-adherence with study drug regimen, etc.)

Failure to comply with Good Clinical Practice (GCP) guidelines will also result in a protocol violation. The Sponsor will determine if a protocol violation will result in withdrawal of a subject.

When a protocol violation occurs, it will be discussed with the investigator and a Protocol Violation Form detailing the violation will be generated. This form will be signed by a Sponsor representative and the Investigator. A copy of the form will be filed in the site's regulatory binder and in the Sponsor's files.

12. Potential Risks

Risk from the device:

Transcutaneous electrical nerve stimulation therapy is considered mostly safe. On rare occasions, an electrical current will be too intense for a subject, causing irritation on the skin. On very rare cases, some subjects have reported some calf muscle cramping with prolonged use.

Some subjects with skin allergies may react to the electrode pads used with the units. People with pacemakers, infusion pumps, defibrillators, and similar devices should not be exposed to the electrical currents produced by transcutaneous electrical nerve stimulation.

Psychological or Social Risks Associated with Loss of Privacy:

In spite of all the safety measures that we will use, we cannot guarantee that the subject's identity will never become known. Every effort will be made to secure the information stored on the mobile application and the information uploaded into the cloud database. In order to maintain subject confidentiality, only a site number, subject number and subject initials will identify all study subjects on any documentation submitted to the Sponsor.

13. Potential Benefits

Subjects enrolled in this study have the potential to have their pain adequately managed while down titrating their overall opioid use. There may be no direct benefit to the subject

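### Exclusion criterion 1 does not reach external infusion pumps, which Section 12's warning appears to cover, and Section 19's adverse event definition is in tension with Section 7.3.5

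*Protocol*

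**What the plan says.** **Devices.** Protocol Section 12 (Potential Risks) says: "People with pacemakers, infusion pumps, defibrillators, and similar devices should not be exposed to the electrical currents" that TENS produces. Exclusion criterion 1 in Section 5 reads: "Subject has a cardiac pacemaker, implanted defibrillator or other implanted electronic device". The other three exclusion criteria concern self-reported data, cellular coverage and clinic visit frequency.

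Section 5 describes subjects with metastatic cancer "with cancer related pain on active chemotherapy treatment", and inclusion criterion 8 requires daily opioid use. At Visit 2 (Section 8.2) staff are told: "Give subject Quell/Sham device, make sure subject properly calibrates". The sham also stimulates. Section 3 states that "the sham device delivers three 2-minute periods of stimulation at 0, 28 and 58 minutes within the therapeutic session".

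**Adverse events.** Section 19 counts an event as an adverse event if it falls in the study period and is judged a direct consequence of study procedures. The next sentence asks for all possible events to go to the sponsoring institute. Section 7.3.5 has adverse events captured throughout the study, with relation to a study drug among the items entered on the CRF. The lists for Visits 2, 3, 4 and 6 and for early withdrawal each tell staff to record adverse experiences, with no causal condition. Section 19's serious event rule has no causal condition either.

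**The concern.** Eligibility criteria are the part of a protocol that formally keeps a subject out. If the risk section names a group who should not receive the current and the criteria do not bar all of that group, protection depends on a staff member noticing the pump and remembering Section 12. The stake is the safety of any such subject.

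The adverse event definition raises a different problem. It places a causality judgement ahead of recording. Suppose a non-serious symptom is put down to chemotherapy or to a change in opioid dose. One coordinator may record it under the visit list and another may omit it under Section 19, and both would be following the protocol. The stake is the completeness of the non-serious safety record, in a trial that Section 19 says has no data safety monitoring board.

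**Working it through.** No power, alpha or event figure is involved, so the check is a comparison of texts.

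**Pump point**

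1. *Scope of the warning.* Section 12 covers pacemakers, infusion pumps, defibrillators and similar devices. The word implanted does not appear.
2. *Scope of the exclusion.* Criterion 1 covers a pacemaker, and otherwise only devices that are implanted.
3. *Overlap.* An implanted electronic pump is caught by the closing catch-all of criterion 1. A pump worn outside the body is not, and no other exclusion criterion touches it. The remainder is external or body-worn pumps, plus any other body-worn device that counts as similar.
4. *Which arm is exposed.* Quell delivers an hour of continuous stimulation per session. The sham delivers 3 × 2 = 6 minutes per session. That is less current time, but not none, so the point applies to both arms.
5. *Other safeguards.*
   - Section 7.1 says "Subjects meeting eligibility criteria will be screened by the primary investigator and treating oncologist". Screening applies the criteria, and the criteria omit external pumps.
   - Section 7.3.1 says "All concomitant medications and concurrent therapies will be documented at screening and each scheduled clinic visit". This may reveal a pump, but it does not bar the subject.
   - Section 11.3 calls it a violation when a party "fails to adhere to significant protocol requirements affecting the inclusion, exclusion, subject safety and primary endpoint criteria". That helps only if someone treats the Section 12 sentence as such a requirement.
   - Section 20 monitoring checks subjects against the eligibility criteria, so the same omission would pass.

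**Adverse event point**

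1. Section 19 makes relatedness a condition of being an adverse event.
2. Section 7.3.5 treats relation as a recorded attribute. That makes most sense if unrelated events are also recorded. It also names a study drug, which this device trial does not have.
3. The visit lists ask for adverse experiences, a term the protocol does not define. They point to wider capture but do not alter the definition.
4. A serious event is reportable under the seriousness criteria whatever its cause. Only non-serious events judged unrelated can drop out.
5. The endpoints in Section 4 and the analyses in Section 10 and SAP Section 2.5 include no adverse event analysis, so no planned estimate or test changes.

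**Two smaller points**

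- The investigator review sentence in Section 19 can be read as confined to events linked to loss of privacy, although Section 11.1 has the investigator follow and treat events that lead to withdrawal.
- A phone-only Visit 5 (Section 8.5) lists only a review of analgesic use. The weekly check-ins in Section 3 are described for device function and troubleshooting, so they do not clearly fill the gap. The interval from Visit 4 to Visit 6 is 10 − 6 = 4 weeks. Section 7.3.5 still requires capture throughout, so the risk is delayed or incomplete recall.

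**The case against.** The strongest reply on pumps is that Section 12 lists them between pacemakers and defibrillators and may mean implanted devices throughout, in which case it matches criterion 1. That reading is available. It does not remove the point, because a contraindication open to two readings needs settling, and the wording as it stands has no such limit. It is also fair that Section 12 is itself protocol text, that staff are trained on the protocol, and that the investigator and oncologist screen each subject. These lower the risk, but none of them is an exclusion.

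A reader might infer from active chemotherapy and daily opioids that external pumps are common here. The documents mention no pump delivery of either and give no prevalence. A reader might also take the absence of a pump item from the Visit 1 and Visit 2 lists as evidence of neglect. Those lists do not name pacemakers or defibrillators either, so this shows only how they are written. Section 16's offer of Quell to sham subjects adds little, since a sham subject with a pump would already have received current.

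On adverse events, a reader might call Sections 19 and 7.3.5 contradictory. The documents do not support that. Section 7.3.5 uses the defined term and may inherit its condition, relation can be graded among related events, and the sentence about all possible events may mean possibly related ones. What stands is that the text does not say which reading governs. In a trial that the protocol describes as carrying minimal physical risk, wanting all-cause capture of non-serious events is also partly a matter of judgement.

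**Conclusion.** Both points hold in a limited form.

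The criteria as written admit a subject with an external or body-worn infusion pump whom Section 12, on its plain wording, says should not be exposed. This rests on reading Section 12 as not confined to implanted devices. The number of such subjects among the planned 40 cannot be stated, and it may be zero.

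The adverse event texts are in tension rather than in strict contradiction, and non-serious events judged unrelated may be left out. How many cannot be stated. A reader might infer that serious event reporting or the trial's efficacy conclusions are weakened. Neither follows, because serious events have their own rule without a causal condition, and no endpoint, sample size or power figure depends on these passages.

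The pump alignment is the more important of the two, because it concerns subject protection directly.

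**What to change.** - **Criterion 1:** extend it to external or body-worn infusion pumps and similar electronic devices, and confirm this before fitting at Visit 2. If only implanted devices are meant, say so in Section 12 instead. Cost: an amendment, one added check and possibly a few more exclusions.
- **Section 19:** define an adverse event as any untoward medical occurrence from consent to week 10, whatever its cause. In Section 7.3.5 and on the CRF, record relation to the device or study procedures as a separate field, in place of study drug. Leave the serious event rule as it is. Cost: more adverse event forms in a sick population.
- **Minor:** reword the investigator review sentence so that it is not confined to loss of privacy, and add an adverse event question to a phone-only Visit 5.

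The SAP is written in the past tense. If conduct is already complete, the sponsor can still report whether any subject with an external pump was enrolled and which adverse event rule staff applied.

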Once the study subjects have started using the device, we will also be able to monitor and track their sleep wirelessly via the mobile application as long as they are wearing the device. Subjects will receive weekly check in's to monitor the functionality of the device and to help troubleshoot any issues with the device for the duration of subject participation in the study. These check-ins will take place in person, by phone, and or per subject's usual outpatient oncology visits. Each subject will use their device for 8 weeks, during which they will continue to track their pain, sleep and frequency of pain medication use as stated above. Study investigators will receive automated alerts via email to ensure that study are participants using their devices and that the devices are powered on at regular intervals for the duration of the study.

Both Quell and the sham device communicate via Bluetooth with the same mobile application. This application provides the subjects with a dashboard of device information, trending data on device usage, and sleep quality. This same information will be synced to a cloud so that investigators involved in the study can collect this data remotely, as well as monitor adherence with the device.

Total duration of subject participation will be 10 weeks.

4. Criteria for Evaluation

Primary Efficacy Endpoint

The primary endpoint is a reduction in daily opioid use assessed at weeks 2, 4, 6, 8 and 10 of the study as recorded by the subject in their analgesia diary. This diary will be a preformatted paper form given to each subject at the start of the study, and will include the name and dosage of all the analgesic pain medications prescribed to the subject, as well as any over the counter pain medications the subject will be using. The subjects will be asked to log what times they take their pain medication each day. This diary will then be reviewed and logged into our secure database at each of the clinic visits as stated above. Per previous studies with a similar design, a 20-30% change in opioid consumption is clinically relevant. This end point is chosen as the overall goal of this study is to provide a novel way for patients with cancer to have optimal pain control while reducing their overall opioid use.

Secondary Endpoints

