for participating in this study. Knowledge gained by conducting this study may lead to the identification of mechanisms that may lead to improved detection and treatment of subjects with cancer related pain.

14. Risk-Benefit Ratio

There is minimal risk of physical harm with any of the devices used. As with any electronic means of communication, no matter how secure, there is always a risk of a data breach.

15. Alternative Treatment(s)

This study involves the addition of a drug free wearable pain device. Subjects may refuse participation in this study and this will not influence their care in any way.

16. Subject Payment/Costs

Subjects will be paid per study visit. Additionally, should they choose, they can keep the Quell device as well as 6 months worth of electrodes. Subjects who were assigned the sham device will be given the option of using and keeping the Quell device.

17. Informed Consent

Informed consent will be obtained in accordance with the Declaration of Helsinki, ICH GCP, US Code of Federal Regulations for Protection of Human Subjects (21 CFR 50.25[a,b], CFR 50.27, and CFR Part 56, Subpart A), the Health Insurance Portability and Accountability Act (HIPAA, if applicable), and local regulations.

The Investigator will prepare the informed consent form, assent and HIPAA authorization and provide the documents to the Sponsor or designee for approval prior to submission to the IRB.

The consent form generated by the Investigator must be acceptable to the Sponsor and be approved by the IRB.

The study personnel that have been trained on this study protocol by the sponsor (investigator, designated co-investigator or research coordinator) will obtain informed consent for this study. Subjects will be given ample time to read and understand the consent form in their native language. Subjects will have an opportunity to ask the investigator and or coordinator questions and have all questions answered before signing. Once the subject has signed the informed consent, a copy will be given to them. The original consent will be filed at the study site.

18. Confidentiality of Data/Privacy of Individuals

Scripps Translational Science Institute affirms the subject's right to protection against invasion of privacy. Data files are stored on a password-protected computer/database and will be accessible only to the above listed investigators and research staff. Subject's data

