will be assigned and identified by a unique code. Traditional identifying information such as name, address, phone, medical record number, etc will not be included in the database. Only the investigators and the research staff will have the link that can match the code to identifying information. Study files will be kept in secure locations at each study site.

19. Safety

Adverse Events:

Any event that occurs during the study period and is considered to be directly related to the study procedures will be considered an adverse event. All possible events will be reported to Scripps Translational Science Institute. Loss of privacy would also be considered a reportable adverse event.

Serious Adverse Events:

We do not anticipate any serious adverse events related to this study. However, events that fit the definition of a serious adverse event according to ICH guidelines must be reported to STSI within 24 hours.

Such events include any untoward medical occurrence that is life threatening, results in death, requires hospitalization or prolongation of existing hospitalization, and/or results in persistent or significant disability/incapacity. Medical Events that may not be immediately life threatening or result in death or hospitalization should also be considered serious when they jeopardize the subject or require intervention to prevent one of the other outcomes listed in the serious definition.

The study Principal Investigator at Scripps will review adverse events and serious adverse events directly related to loss of privacy. This study does not have a Data Safety Monitoring Board.

20. Monitoring

STSI will monitor the study throughout its duration. The study monitor will visit the site at appropriate intervals to review investigational data for accuracy and completeness and to ensure adherence with the protocol. The investigator/site will permit access to all documents and records maintained on the subjects in the study. Source documents will be reviewed to ensure all subjects have properly signed and dated the informed consent/HIPAA forms. All information will be reviewed to ensure eligibility criteria as per the protocol, and supporting source data will be verified. The Investigator and/or research coordinator must be available for monitoring visits. STSI will collect the appropriate regulatory document records at the site will also be reviewed periodically during monitoring visits for accuracy and completeness.

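### Lower opioid use is the primary endpoint, yet no risk from it is listed and its non-serious harms can go uncounted under Section 19

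*Protocol*

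**What the plan says.** **The intended effect.** Protocol Section 4: "The primary endpoint is a reduction in daily opioid use assessed at weeks 2, 4, 6, 8 and 10 of the study". Section 5 requires every participant to meet this criterion: "Subject using at least one opioid medication on a daily basis". Section 13 names the benefit: "Subjects enrolled in this study have the potential to have their pain adequately managed while down titrating their overall opioid use". It then adds that a subject may get no direct benefit.

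**The stated risks.** Section 12 has two headings, the device and loss of privacy. The device part opens with "Transcutaneous electrical nerve stimulation therapy is considered mostly safe" and goes on to skin irritation, calf cramping, electrode allergy and implanted devices. Section 14 says "There is minimal risk of physical harm with any of the devices used" and adds only the possibility of a data breach.

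**Where opioid reduction sits.** Section 15: "This study involves the addition of a drug free wearable pain device". Section 6: "Any changes in medication type, doses and frequency should be discussed with the treating physician and documented". None of the visit lists in Section 8 contains a step for reducing opioids.

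**What is counted.** Under Section 19, an event during the study that is "considered to be directly related to the study procedures will be considered an adverse event". Serious events are defined separately in that section, by outcome and without a relatedness condition, and go to the sponsor within 24 hours. Section 7.3.5 captures adverse events throughout. It gives no definition of its own and asks for the relation to a study drug, although the trial tests a device. The supplied SAP text (Section 2.5) describes no safety analysis.

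**The concern.** If a trial sets out to lower opioid use in people with metastatic cancer who take opioids daily, the foreseeable harms of its own effect are lost pain control and symptoms that follow taking less. The risk statement counts the reduction as a benefit and nowhere as a possible harm.

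The adverse-event definition then depends on a link to study procedures. Because reduction is the aim but not a procedure, a non-serious event caused by it can reasonably be judged to fall outside the definition. This can happen in both arms, since sham subjects who believe they are being treated may also cut back.

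What is at stake is the safety half of the conclusion. A statement that Quell lowers opioid use at minimal risk would rest on a count that may leave out the harm most closely tied to the benefit. The primary opioid comparison itself is not affected.

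**Working it through.** **The plan's own figure.** The only quantity the Protocol gives on the intended effect is in Section 10: a 20-point difference in mean percent change, 20 per group, two-sided t-test at 0.05. The noncentrality is difference / (SD × √(2/n)), with 38 degrees of freedom.
- SD 22: 20 / (22 × √0.1) = 2.87, power 80.0% (stated 80%).
- SD 19: 20 / (19 × √0.1) = 3.33, power 90.0% (stated 90%).

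Both reproduce. SAP Section 2.5 pairs the powers and SDs the other way round, which does not reproduce; that is a separate matter.

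**Following a non-serious event through the text.** Suppose a subject takes less opioid and then has symptoms.
1. Sections 12 and 14 do not name the event as a risk, so nothing prompts staff to look for it.
2. Visits 3, 4 and 6 and the early withdrawal visit have a general adverse-experience step. None mentions events after a reduction.
3. The phone form of Visit 5 lists diary review only. That contact can reveal a fall in opioid use but has no adverse-event step.
4. If the event is mentioned, Section 19 makes it adverse only if someone judges it directly related to a study procedure. Section 7.3.5 uses the same term and does not widen it.
5. Section 19 words the principal investigator's review around events related to loss of privacy, and there is no Data Safety Monitoring Board. A later check is therefore not assured.
6. No by-arm safety table is described in the Protocol or the supplied SAP text.

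**What partial counting does.** The documents give no rate for these harms and no counting fraction, so both are assumed here. Let p be the true proportion of subjects affected in an arm of 20 and c the chance that a case is counted, independently between subjects. The chance of recording none is (1 − p × c)^20. With p = 20%:
- c = 1: (1 − 0.20)^20 = 1.2%
- c = 1/2: (1 − 0.10)^20 = 12.2%
- c = 1/4: (1 − 0.05)^20 = 35.8%

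**What full counting could show.** With 0 cases in 20 and every case counted, the one-sided 95% upper limit is 1 − 0.05^(1/20) = 13.9%. This follows from the sample size, and better recording would not change it. It does show how little a zero proves even when it is a true zero.

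**The case against.** The case against is substantial, and much of it stands.

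- **Serious events are covered.** Section 19 includes any that meet the seriousness criteria, also those needing intervention to prevent such an outcome. A reader might infer that harms of reduction need not be counted at all, or that zero could be reported whatever the true rate. For serious events that is wrong.
- **Pain and several symptoms are measured.** Pain is scored twice daily in the app, and the SF-MPQ-2 is repeated. The EORTC form at weeks 0, 6 and 10 asks about pain, sleep, nausea, tension and depression. Section 10 compares pain and quality of life between arms over time. Worse pain would be seen, but as an efficacy mean, not as a count of subjects harmed.
- **The raw data for a link exist.** Adverse events carry start and stop times, and the diary logs dose times. This helps only for events that have been recorded.
- **No taper is directed.** A reader might take Section 13 to mean that the study reduces opioids. The text speaks only of potential, and Sections 6, 13 and 15 can be read together as a device added to usual care. They leave unsaid whether reduction belongs to the study.
- **The relatedness field and the instruction to report all possible events** hint at wider capture. Neither changes the definition.

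A reader might also infer from the 20-point difference that about half of the 40 subjects are meant to reduce. That does not follow: a difference in means fixes no number of reducers, and rising use in the sham arm could contribute to it. Nor can omission from the consent form be inferred, because those pages are not available.

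**Conclusion.** The point holds for non-serious harms. The protocol treats lower opioid use as endpoint and benefit, lists no risk from it, and defines non-serious adverse events so that its consequences can be left out. Worse pain is captured only as efficacy. Withdrawal-type symptoms that the scales do not ask about may not be captured at all.

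The size cannot be fixed from the documents. Under the assumed 20% rate, the chance of an empty count in an arm rises from about 1% to between 12% and 36% as counting falls to a half or a quarter. These figures assume independent cases and are illustrations, not estimates.

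The conclusion rests on reading Section 19 as the operative definition and on the SAP text supplied. A safety analysis elsewhere would narrow the point but would not repair the definition. This should be changed: it is a stated rule that gives an incomplete safety result, not merely a missing detail.

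**What to change.** 1. Reconcile Section 19 with Section 7.3.5 so that any untoward event during the study is recorded regardless of attribution. Record relatedness to the device (in place of a study drug) and to a change in opioid use as separate fields.
2. Ask every subject in both arms the same adverse-event question, covering loss of pain control and symptoms after taking less opioid. Ask it at every contact from Visit 3 to Visit 6, including the phone form of Visit 5, and at early withdrawal. Ask whether or not the diary shows a fall: questioning only those with a fall would tie ascertainment to the primary outcome and make the arms non-comparable if the device works.
3. Tabulate these events by arm beside the primary result, and say so in the SAP.
4. Add the risk to Sections 12 and 14. State consistently across Sections 6, 13 and 15 whether opioid reduction is part of the study or left to usual care, and check that the consent text agrees.

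No dose or clinical rule is proposed. The cost is an amendment, one question at existing contacts and one table. The downside is slightly longer contacts and more recorded events, many of them unrelated in this population.
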